1.1 Demographic and clinical data

The prevalent CKD stage 3 – 5 population will be screened by the researcher. After verification of the in- and exclusion criteria, eligible patients will be invited to participate the HORUZ study, with approval of their treating nephrologist. After signing the informed consent, data at baseline and during followup visits will be collected on paper clinical report forms (Table 1). Hypertension is defined as an office BP \geq 140/90 mmHg or home BP \geq 130/80 mmHg, or current medication for hypertension.¹ Diabetes mellitus will be assumed to be present in patients who report use of insulin and/or oral hypoglycemic agents. CV diseases include coronary artery disease, as documented by coronary angiography or a history of myocardial infarction, congestive heart failure, cerebrovascular accident, or known peripheral vascular disease. Fluid assessments, including BIS measurements, will be recorded on the HORUZ registration form (Appendix).

The healthy controls included for the cross-sectional analysis will only be followed according to visit 0 and 1.

| | Baseline Visit 0 | Month 1 Visit 1 | Month 3 Visit 2 | Month 6 Visit 3 | Month 9 Visit 4 | Month 12/ end of study Visit 5 |
|--|---------------------|--------------------|--------------------|--------------------|--------------------|-----------------------------------|
| Consent | х | | | | | |
| Demographics: Age (y) Gender Height (cm) Smoking status Etiology CKD Hypertension Diabetes CV disease Tx list | x | | | | | |
| eGFR _{creat} | x | x | x | x | x | x |
| CrUrCl | | x | x | x | x | x |
| 24h urine | | x | x | x | x | x |

Table 1 Schedule of the main data to collect in CKD subjects.

| BP | x | | x | x | x | x |
|-----------------|---|---|---|---|---|---|
| ECG | x | | x | x | x | x |
| Echo cor | | x | | | | x |
| CV events | | x | x | x | x | x |
| Hospitalization | | x | x | x | x | x |
| Medication | x | | x | x | x | x |
| Whole body BIS | x | | x | x | x | x |
| Thoracic BIS | x | | x | x | x | x |
| SF36 | x | | | | | x |
| Adverse event | | x | x | x | x | x |

Abbreviations: BIS, bioimpedance spectroscopy; BP, blood pressure; CKD, chronic kidney failure; Creat, creatinine; CrUrCl, mixed creatinine

and urea clearance; CV, cardiovascular; ECG, electrocardiography; M, month; SF36, short form 36 questionnaire; Tx, transplantation.

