1.2 Primary endpoint

The association between fluid status and kidney function decline in patients with CKD stage 3 (CKD-EPI 60-30ml/min), 4 (CKD-EPI 30-15ml/min) and 5 (CKD-EPI < 15 ml/min) is the primary objective of the HORUZ study.

The primary endpoint is the mean eGFR decline which will be compared between the FO-group and the non-FO-group. BIS-measured FO will be expressed as overhydration (OH) normalized to ECW and noted as a percentage of ECW (OH/ECW).^{6,44} FO is defined as an OH/ECW \geq 7% (or an absolute OH \geq 1.1 L).⁴⁵

Rate of kidney function decline will be assessed by the slope in eGFR_{creat} CKD-EPI (see formula below), defined as the regression coefficient between eGFR_{creat} and time, in units of mL/min/1.73m² per year. At least 3 eGFR_{creat} values are required to evaluate eGFR_{creat} slope. All eGFR_{creat} CKD-EPI will be uniformly calculated in the laboratory. eGFR_{creat} decline is assessed by changes in eGFR over time. Rapid eGFR_{creat} decline is defined as the quartile with the steepest eGFR slope (eGFR_{creat} decline > $3mL/min/1.73m^2$ per year).⁹

Investigating the Hemodynamic profile Of chronic Renal patients by Use of Bioimpedance HORUZ study

 $eGFR_{creat} = 141 \times min(S_{creat}/\kappa, 1)^{\alpha} \times max(S_{creat}/\kappa, 1)^{-1.209} \times 0.993^{Age} \times 1.018$ [if female] × 1.159 [if black]

 $\begin{array}{l} S_{creat} \left(standardized \ serum \ creatinine \right) = mg/dL \\ \kappa = 0.7 \ (females) \ or \ 0.9 \ (males) \\ \alpha = -0.329 \ (females) \ or \ -0.411 \ (males) \\ min = indicates \ the \ minimum \ of \ S_{creat}/\kappa \ or \ 1 \\ max = indicates \ the \ maximum \ of \ S_{creat}/\kappa \ or \ 1 \\ age = years \end{array}$

Average CrUrCl will be determined by creatinine and urea measurements in blood- and urine samples (Table 2).

Residual urine output (mL per 24h) will be collected every study visit and analyzed on volume, urea, creatinine, sodium, osmolarity and albumin/creatinine ratio (ACR) (Table 2).

Time to renal replacement therapy will be recorded.

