| Ferritin | | | |
| 24 urine collection | | | |
| Quantity | Urine | No | Every study visit |
| Creatinine | | | |
| Urea | | | |
| Sodium | | | |
| Albumin | | | |
| Protein | | | |

2. Randomization

Not applicable.

3. Study procedures and interventions

After inclusion during the baseline visit, a research visit will be scheduled every 3 months until end of study or withdrawal. Study visits will be scheduled as much as possible before the regular visit to the treating nephrologist. During this period of follow up, all participants will undergo the following procedures to determine the predefined research parameters (Table 1):

At the first visit, patient's medical file will be checked for baseline demographic information, comorbidities, risk factors and medication use. Patients will be asked about complains or symptoms related to fluid homeostasis (weight gain, shortness of breath, thoracic pressure, palpitations, muscle cramps, dizziness, fatigue, thirst, obstipation). Physical signs of fluid imbalance (subcutaneous edema) will be evaluated by physical examination. Subjects will be requested to collect 24h urine sample and take a blood sample to determine the mixed urea and creatinine clearance. BP, ECG and echocardiography will be performed in all subjects. BIS will be performed by the reference and wearable device. Patients will be asked to fulfill the SF36 questionnaire.

During subsequent visits, anamnesis, physical examination, blood- and urine samples, BP and BIS measurements will be taken from all subjects.

At 3 and 12 months of follow up, additional evaluation of cardiac function and quality of life will be performed.

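### The primary eGFR slope has no cut-off at dialysis or transplantation, so by default readings taken after renal replacement therapy enter it

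*Combined protocol and SAP*

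**What the plan says.** Methods 1.2 states: "The primary endpoint is the mean eGFR decline which will be compared between the FO-group and the non-FO-group". The slope is "defined as the regression coefficient between eGFR_{creat} and time", per year. The only rule on which values count is "At least 3 eGFR_{creat} values are required to evaluate eGFR_{creat} slope". The same section adds "Time to renal replacement therapy will be recorded"; no analysis of that time is described.

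Table 1 schedules eGFR at all six visits: baseline and months 1, 3, 6, 9 and 12. Methods 3 says "a research visit will be scheduled every 3 months until end of study or withdrawal", and that at subsequent visits "blood- and urine samples, BP and BIS measurements will be taken from all subjects". Methods 4 lets the investigator withdraw a subject for urgent medical reasons and does not name RRT. It also schedules a closing visit at withdrawal with the visit 5 measurements, which include eGFR. The Statistical Analysis section keeps drop-outs' measurements up to withdrawal and mentions neither dialysis nor transplantation.

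The inclusion criteria require non-dialysis status at entry. Stage 5 patients are eligible, and transplant-list status is collected at baseline.

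**The concern.** RRT during the 12 months is foreseeable, and the plan itself expects to record it. Once it starts, serum creatinine reflects dialysis or a graft as well as the patient's own kidneys, so eGFR computed from it no longer describes native decline. A slope fitted through pre- and post-RRT values mixes two quantities.

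The error need not be balanced between groups. The Hypothesis section expects FO patients to lose function faster. If they do, more of them reach RRT, and more of their slopes are flattened or reversed. That pulls the primary difference toward zero and adds outliers that widen its standard error. The rapid-decline class in 1.2 (loss above 3 mL/min/1.73m² per year) is exposed in the same way.

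**Working it through.** **1. The plan's own figure.** Sample size section: difference 2 per year, SD 4.7, alpha 0.05 (taken as two-sided), power 0.80.

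n per group = 2 × [4.7 × (1.960 + 0.842) / 2]² = 86.7. The plan states 86, which gives 79.7% power. The figure reproduces, so 2.0 and 4.7 serve as the reference below.

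**2. One patient on the Table 1 visit times** (values assumed). Baseline eGFR 11, true slope -6 per year, RRT after month 6. Readings to month 6 are 11, 10.5, 9.5 and 8.

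The mean visit time is 31/6 = 5.17 months, and the sum of squared deviations is 110.83 months². Fitted slope = 12 × Σ(time deviation × eGFR) / 110.83.

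| Readings at months 9 and 12 | Σ(deviation × eGFR) | Fitted slope per year |
|---|---|---|
| Continue the earlier decline (6.5, 5) | -55.4 | -6.0 |
| Plateau at 8 | -29.2 | -3.2 |
| Dialysis readings of 10 | -7.8 | -0.8 |
| Transplant, readings of 45 | +365.5 | +39.6 |

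The four pre-RRT values alone give -6.0. One such transplant moves the mean of an 86-patient group by (39.6 + 6.0)/86 = 0.53, about a quarter of the target difference.

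**3. If this patient were withdrawn at RRT start.** The closing visit can still add a reading. With values at months 0, 1, 3, 6 and 7, and a reading of 10 at month 7 in place of the 7.5 on the true line, the sum of squares is 37.2. The slope is then -6 + 12 × (3.6 × 2.5)/37.2 = -3.1.

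**4. Effect on the group difference.** Let f be the excess share of the FO group starting RRT and D the upward shift in their slopes. The difference becomes 2 - fD, and the FO-group variance becomes 4.7² + f(1 - f)D². For f = 5% and 86 per group:

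- D = 4: difference 1.8, SE = √[(22.09 + 22.85)/86] = 0.72, power 70%.
- D = 8: difference 1.6, SE = √[(22.09 + 25.13)/86] = 0.74, power 58%.

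**5. Simulation over stage mix.** Assumptions: 86 per group, mean slopes -5 and -3 (true difference 2.0), total slope SD 4.7, residual SD 2, RRT when eGFR falls below 8, dialysis readings of 8 to 10, transplant readings of 45.

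| Share in stage 5 | Dialysis only | 10-20% of RRT by transplant |
|---|---|---|
| 20% | about 1.7-1.8 | about 1.4-1.7 |
| 5-10% | about 1.8-1.95 | about 1.7-1.9 |

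With 20% in stage 5, about 12 FO and 8 non-FO patients per 86 start RRT, an excess of 4/86 = 4.7 percentage points, close to the 5% in step 4. Restricting the slope to pre-RRT values returns about 1.9-2.0.

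**The case against.** The strongest objection is that silence is not a rule. A reader might infer that the plan instructs the analyst to use post-RRT values. No sentence says so. The population is described as not on dialysis, Table 1 and the registration form allow an end-of-study visit before month 12, and an investigator might treat RRT start as a withdrawal, after which the data are cut. This stands as a limit on the wording: inclusion is the default that follows from an unrestricted slope and a schedule covering all subjects. It does not remove the gap. RRT is not a stated withdrawal reason, and the closing visit could still supply a post-RRT value.

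A reader might also infer that the fastest decliners throughout the cohort lose their steep slopes. That is too broad. With an RRT threshold of 8, a patient entering at eGFR 30 would have to lose more than 22 within the year to be affected. The patients concerned are mainly those in stage 5 and low stage 4; steep slopes in stage 3 are essentially untouched.

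Nor do the documents support a claim that the primary result must be badly distorted. Reversal is certain only with a working transplant. Dialysis flattens a slope only if readings stop following the earlier decline. The lowest estimates need both a 20% stage 5 share and a material number of transplants within 12 months.

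**Conclusion.** The concern holds as a gap in the definition of the primary endpoint: no cut-off at RRT is stated, and following the text as it stands brings post-RRT values into the slope. The direction, toward no difference, depends on RRT being more frequent in the FO group, which the study's own hypothesis implies.

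The attenuation ranges from slight (about 1.95 instead of 2.0) to material (about 1.4), depending on stage mix, RRT frequency, transplant share and post-RRT creatinine. None of these is in the documents, so no single figure should be quoted. It should be corrected before analysis, because otherwise the choice of readings could be made after seeing the data.

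**What to change.** In Methods 1.2 and the Statistical Analysis section, state that only eGFR values before the start of dialysis or transplantation enter the primary analysis. The last value before RRT is included, and any end-of-study value after RRT start is excluded.

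A cut-off alone is not enough. RRT before the month 3 visit leaves only the baseline and month 1 values, and the three-value rule would then drop that patient. Estimate the slope difference with a linear mixed model (FO group by time), in which short series still contribute.

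Report time to RRT by FO group descriptively, as cumulative incidence with death as a competing event.

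No new visits or data items are needed for the cut-off, since the RRT date is already recorded. There are costs. The model replaces the per-patient slope and the repeated-measures ANOVA, so it changes the primary analysis and is more than a clarification. Patients who start RRT contribute shorter series. With perhaps 12 against 8 events per 86 under the assumptions above, and fewer with less stage 5, the time-to-RRT comparison will be imprecise.

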1.3 Secondary endpoints

The secondary objective is to identify the clinical factors associated with FO during a longitudinal follow up. Secondary outcomes of interest are the central volume status (measured by echocardiography and thoracic BIS in combination with photoplethysmography), BP, the cardiac systolic and diastolic function, CV events, hospitalizations, inflammatory- and nutrition status, and quality of life, between CKD stages 3, 4 and 5.

- 1. *Cardiac function:* Electrocardiography and echocardiography (see point 3.3) will be scheduled at baseline, and at 12 months or at end of study visit.
- Thoracic BIS values: a wearable device from Imec Eindhoven will be used to measure thoracic
 BIS values in combination with photoplethysmography and cardiopulmonary index.
- 3. *Blood pressure:* patients will be asked to take BP measurements at home three times a week twice daily with an automatic BP monitor. Mean arterial pressure corrected for heart

frequency will be calculated. BP measurements can be transmitted to the researcher by use of the local Dharma platform.

- 4. *CV events:* CV events defined as hospitalization for coronary disease, heart failure, stroke or peripheral artery disease will be recorded during follow-up.
- 5. *Hospitalization rate and indication:* hospitalization rate and indication will be listed.
- 6. *Inflammatory- and nutrition status:* CRP, ferritin and albumin will be determined every visit (Table 2). Fat tissue mass and lean tissue mass will be analyzed by BIS measurements.
- 7. *Quality of Life assessment:* SF36 questionnaire will be filled in at baseline and end of study visit.

| Table 2 Overview of | f parameters evaluatir | g kidney function, r | enal metabolism a | and inflammation in HORUZ study. |
|---------------------|------------------------|----------------------|-------------------|----------------------------------|

| Assay | Material | Standard care | Frequency |
|-------------------------|--------------|---------------|-------------------|
| Residual renal function | | | |
| Urea | Plasma/serum | yes | Every study visit |
| Creatinine | | | |
| Metabolism and electrol | ytes | | |
| Hemoglobin | Plasma/serum | yes | Every study visit |
| Sodium | | | |
| Potassium | | | |
| Bicarbonate | | | |
| Phosphate | | | |
| Calcium | | | |
| NT-proBNP | | No | Every study visit |
| Inflammation | | | |
| C-reactive protein | Plasma/serum | yes | Every study visit |
| Leucocytes | | | |
| Albumin | | | |
| Ferritin | | | |
| 24 urine collection | | | |
| Quantity | Urine | No | Every study visit |
| Creatinine | | | |
| Urea | | | |
| Sodium | | | |
| Albumin | | | |
| Protein | | | |

2. Randomization

Not applicable.

3. Study procedures and interventions

After inclusion during the baseline visit, a research visit will be scheduled every 3 months until end of study or withdrawal. Study visits will be scheduled as much as possible before the regular visit to the treating nephrologist. During this period of follow up, all participants will undergo the following procedures to determine the predefined research parameters (Table 1):

At the first visit, patient's medical file will be checked for baseline demographic information, comorbidities, risk factors and medication use. Patients will be asked about complains or symptoms related to fluid homeostasis (weight gain, shortness of breath, thoracic pressure, palpitations, muscle cramps, dizziness, fatigue, thirst, obstipation). Physical signs of fluid imbalance (subcutaneous edema) will be evaluated by physical examination. Subjects will be requested to collect 24h urine sample and take a blood sample to determine the mixed urea and creatinine clearance. BP, ECG and echocardiography will be performed in all subjects. BIS will be performed by the reference and wearable device. Patients will be asked to fulfill the SF36 questionnaire.

During subsequent visits, anamnesis, physical examination, blood- and urine samples, BP and BIS measurements will be taken from all subjects.

At 3 and 12 months of follow up, additional evaluation of cardiac function and quality of life will be performed.

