In order to investigate this hypothesis, we want to perform the HORUZ study. We are interested in the fluid status, BP and thoracic BIS signal of patients with CKD 3 - 5, not on dialysis. We aim to provide more evidence to further support the frequent use of BIS in diagnostic guidelines of patients with CKD.

OBJECTIVES

The primary objective of the HORUZ study is to associate fluid status with kidney function decline in patients with CKD stage 3 (CKD-EPI eGFR 60-30ml/min), 4 (30-15ml/min) and 5 (< 15 ml/min) and compare them to an age- and sex- matched healthy control group. Primary outcome is the mean eGFR decline which will be compared between the FO-group and the non-FO-group.

The secondary objective is to identify the clinical factors associated with FO during a longitudinal follow up. Secondary outcomes of interest are the central volume status (measured by echocardiography and thoracic BIS in combination with photoplethysmography), the cardiac systolic and diastolic function, CV events, hospitalizations, inflammatory- and nutrition status, and quality of life, between CKD stages 3, 4 and 5 and compare them to an age- and sex- matched healthy control group.

STUDY DESIGN

The HORUZ study is a non-randomized trial with intervention of regular BIS- and BP measurements, blood- and urine sampling. Prevalent patients with CKD stages 3, 4 and 5 and an age- and sex- matched healthy control group will be included. Inclusion period will last 18 months and CKD-patients will be followed up for 12 months.

STUDY POPULATION

1. Population

206 patients with CKD stages 3-5 will be included from the outpatient clinic of Ziekenhuis Zuid-Oost Limburg in Genk (Belgium).

A healthy control group for the cross-sectional part will be recruited through visitors and/or personnel of Ziekenhuis Oost-Limburg in Genk (Belgium).

2. Inclusion criteria

In order to be eligible to participate in this study, a subject must meet the following criteria:

- Prevalent non-dialysis patients with eGFR < 60 ml/min (for CKD subjects)
- Age > 18 years
- Signed informed consent

3. Exclusion criteria

A subject who meets any of the following criteria will be excluded from participation in this study:

- Acute kidney injury
- eGFR < 20ml/min directly post-nephrectomy
- Clinical conditions affecting BIS measurements: limb amputation, impaired skin integrity, brain stimulator, pacemaker with low threshold or unipolar pacemaker.

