2.3 Suspected unexpected serious adverse reactions (SUSAR)

Not applicable.

3. Follow-up of adverse events

AE according to the study are considered very unlikely, due to the fact that only non-invasive methods are used. All AEs will be followed until a stable situation has been reached and treated to standard procedures.

4. Data Safety Monitoring Board (DSMB)

Not applicable.

STATISTICAL ANALYSIS

A table with baseline characteristics of all subjects will be provided. Baseline characteristics of the population will be expressed as the mean \pm standard deviation if normally distributed, or as the median [25th – 75th percentile] as not normally distributed, for continuous and dichotomous data, and as the frequency (%) for categorical data. Measurements of drop-outs will be included until the moment of withdrawal from the study. Normality in distribution will be tested by the Shapiro-Wilk statistic. Repeated measurements ANOVA techniques will be used for analysis. Pearson's Chi-squared test will be used to assess whether there is any distinction between subgroups in rate of kidney function decline. In case the analysis of the baseline characteristics showed any clinically relevant imbalance, we will also perform a multivariable logistic regression analysis in order to correct for this imbalance. Differences in LVH will be corrected for systolic BP and haemoglobin, as these are predictors of LVH in predialysis population.¹⁵ Depending on the level of measurement a Chi-squared test or a T-test will be used to assess differences in secondary study parameters, and logistic and linear regression for baseline-corrected estimates. Tests will be considered significant if p-values are ≤ 0.05 .

ETHICAL CONSIDERATIONS

1. Regulation statement

The study will be conducted according to the principles of the Declaration of Helsinki (Fortaleza, Brasil, 2013).

2. Recruitment and consent

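### No named method fits the longitudinal fluid-overload objective: repeated yes/no FO needs a patient-clustered model, and pooling visits in the named tests would inflate type I error for patient-level factors

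*Combined protocol and SAP*

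**What the plan says.** - **Objective.** Methods, section 1.3: "The secondary objective is to identify the clinical factors associated with FO during a longitudinal follow up". The Summary and the Objectives section say the same.
- **Outcome.** Section 1.2 makes FO a threshold state: "FO is defined as an OH/ECW" of at least 7%, or absolute OH of at least 1.1 L. The same section also expresses OH as a percentage of ECW, so a continuous form exists.
- **Measurements.** Table 1 schedules whole body BIS at months 0, 3, 6, 9 and 12, and not at month 1. BP and medication are recorded at the same five visits. Table 2 lists the laboratory values for every study visit.
- **Size.** "206 patients with CKD stages 3-5 will be included", and "CKD-patients will be followed up for 12 months".
- **Methods.** The Statistical Analysis section says: "Repeated measurements ANOVA techniques will be used for analysis". It attaches no outcome to that sentence. For secondary parameters it says: "Depending on the level of measurement a Chi-squared test or a T-test will be used to assess differences in secondary study parameters", and adds "logistic and linear regression for baseline-corrected estimates". It keeps the measurements of patients who drop out up to the time they withdraw. It mentions no mixed model, GEE or cluster-robust variance.

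The plan does not say whether FO for this objective is taken at baseline, visit by visit, as a change or over all visits. It also does not say whether FO is analysed as binary or continuous.

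**The concern.** The question is longitudinal and the outcome is a repeated yes/no state, so records from one patient are correlated. Several candidate factors (BP, medication, laboratory values) change from visit to visit, and some patients will have incomplete follow-up. An analyst who follows the plan has three routes:

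- put all visits into a test that assumes independence;
- reduce each patient to one record;
- use repeated measures ANOVA on a different form of the outcome.

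The first route makes p-values and confidence intervals wrong, in a direction that depends on the factor. The second discards most of the repeated data. The third leaves FO status itself, the time-varying factors and the incomplete patients without an analysis. What is at stake is which factors the study reports as associated with FO, and that is its stated secondary objective.

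**Working it through.** **Plan's own figure.** The plan gives none for this objective. Its only sample size is for the primary endpoint. With difference 2, SD 4.7, two-sided alpha 0.05 and power 0.80, 2 × [4.7 × (1.96 + 0.84) / 2]² = 86.6 per group, against the stated 86. This does not bear on the present point.

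**Inputs.** N = 206 patients (Study Population). m = 5 whole body BIS visits (Table 1). Maximum records 206 × 5 = 1,030. The documents give no within-patient correlation of FO (ICC), so a range is assumed.

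**Visits pooled as independent, factor constant within patient.**

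- Design effect: DE = 1 + (m − 1) × ICC = 1 + 4 × ICC.
- True type I error of a nominal 5% test: 2 × [1 − Φ(1.96 / √DE)].
- Equivalent number of independent records: 1,030 / DE.

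| Assumed ICC | DE | True SE / naive SE (√DE) | Equivalent records | Type I error |
|---|---|---|---|---|
| 0.2 | 1.8 | 1.34 | 572 | 14% |
| 0.3 | 2.2 | 1.48 | 468 | 19% |
| 0.5 | 3.0 | 1.73 | 343 | 26% |
| 0.7 | 3.8 | 1.95 | 271 | 31% |

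**Does the type of factor matter?** A simulation with no true association used 206 patients, 5 complete visits, a random patient intercept and 1,000 runs per setting. FO prevalence was set at 50%, in line with the overhydration estimate in the Introduction. Three strengths of the patient effect gave observed ICCs of about 0.29, 0.54 and 0.74. Rejection rates at nominal 5%:

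| Factor | Pooled logistic, naive SE | Pooled logistic, cluster-robust SE |
|---|---|---|
| Constant within patient | 19.7%, 26.2%, 33.4% | 4.4%, 5.1%, 5.6% |
| Half its variance between patients | 11.4%, 16.1%, 21.8% | 5.2%, 4.2%, 5.4% |
| Varies only within patient | 3.1%, 0.1%, 0.0% | 6.9%, 5.5%, 5.6% |

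With one visit per patient (first two factor types), ordinary logistic regression rejected in 4.6% to 5.2% of runs, so it is valid.

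**Cost of using one visit.** 206 × 4 = 824 of the 1,030 scheduled records are unused. For a patient-level factor, the SE from a correct five-visit analysis relative to a single visit is about √(DE / 5). This is 0.60, 0.66, 0.77 and 0.87 at ICC 0.2, 0.3, 0.5 and 0.7. The gain from using all visits is therefore real but shrinks as FO becomes more stable within patients.

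**Fit of each named method to repeated binary FO.**

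- Chi-squared, t-test and ordinary regression make no allowance for correlation.
- Repeated measures ANOVA allows for correlation, but it models a continuous outcome, in its classical form needs complete visits, and does not naturally take covariates that change over time.

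**The case against.** A reader might infer that every named method assumes independence, and that the standard errors for this objective will therefore be too small. The documents do not support that, for three reasons.

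1. Repeated measures ANOVA is named in the same paragraph and does model within-patient correlation. Applied to OH/ECW with sex, diabetes or CV disease as between-patient factors, it would be a legitimate analysis in patients with complete visits.
2. The plan nowhere says that visits will be stacked as independent records. It treats FO and non-FO as patient groups for the primary endpoint, and regression with baseline correction may well mean one follow-up value per patient.
3. Even under pooling the direction depends on the factor. Naive standard errors are too small for factors that are constant or largely between patients, and too large for factors that vary only within patients.

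Nor does using one record per patient necessarily leave the objective unanswered. FO at any follow-up visit, new FO by month 12, or baseline factors against month-12 FO are longitudinal questions that ordinary logistic regression can handle.

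All of this stands, and it limits the claim. It does not supply the missing analysis. The plan chooses none of these summaries. They cannot use the repeated BP, medication and laboratory values visit by visit, and a summary such as FO at any visit depends on how many visits a patient completed. ANOVA still does not cover binary FO, time-varying factors or partial follow-up, although the plan retains the data of patients who drop out.

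**Conclusion.** The point holds as a mismatch between the objective and the methods, not as a demonstrated error in standard errors. No analysis is assigned to the longitudinal FO objective, and none of the named methods fits repeated binary FO with time-varying factors and incomplete follow-up.

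The type I error of about 14% to 31% rests on three conditions: all five visits are pooled as independent, the factor is constant within patient, and the within-patient correlation lies between 0.2 and 0.7. The correlation is an assumption and the pooling is one possible reading of the plan. Under the same pooling, tests of purely within-patient factors would be conservative. With one visit per patient the error rate is about 5%, and the loss is in unused data.

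**What to change.** In the Statistical Analysis section, assign one pre-specified patient-clustered model for FO status to this objective. It should use all available visits, with visit as a factor and time-updated BP, medication and laboratory values. Name the candidate factors and say which are time-varying. Add a linear mixed model for OH/ECW as the companion analysis.

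Choose one of two models and state what it estimates:

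- a random-intercept logistic model, which gives patient-specific associations; or
- a logistic GEE with robust standard errors, which gives population-averaged associations.

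The two are not interchangeable. If GEE is used with time-updated covariates, specify an independence working correlation or justify another. The Introduction treats FO as both a cause and a result of renocardiac complications, and under such feedback other working correlations can bias the estimates.

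The cost is small: a few sentences, standard software, slightly more analysis work, and no new data or visits. Confidence intervals for patient-level factors will be wider than a naive pooled analysis would give.
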